7.2.5 Sample Collection and Handling

The actual dates and times of sample collection must be recorded in the eCRF or laboratory requisition form. If blood samples are collected via an indwelling cannula, an appropriate amount (1 mL) of serosanguineous fluid slightly greater than the dead space volume of the lock will be removed from the cannula and discarded before each blood sample is taken. Refer to the Schedule of Events (*Table 7.3*) for the timing and frequency of all sample collections.

For samples collected from the central laboratory, sample dates and times must be recorded on the laboratory requisition form. Further instructions for the collection, handling, storage, and shipment of samples are found in the laboratory manual that will be provided. Collection, handling, storage, and shipment of samples must be under the specified, and where applicable, controlled temperature conditions as indicated in the laboratory manual.

Table 7.3: Schedule of Events

Following the positive primary analysis some of the below procedures have been adjusted (PD evaluation, PK/Immunogenicity). For more details on the updated procedures, please refer to [Section 7.2.4](#).

Note: Refer to [Appendix 12](#) for a description of study procedures for subjects who continue to receive study treatment after the CCO for the final OS analysis until subjects meet treatment discontinuation criteria (see [Section 5.3.1](#)) or until study treatment is available through another source such as commercial availability with reimbursement, continued access through a long-term extension study, a patient access program, or after the last subject transitions into the long-term extension phase of the study up to 30 September 2024, whichever occurs first. No eCRF data will be collected after the CCO for the final OS analysis.

Day of Cycle (28-days)	Screening	Treatment: visit window during the treatment period is +/- 3 days												Survival follow-up Every 12 weeks 8 weeks After Last Dose	
		Cycles 1 and 2				Cycles 3-6				Cycles 7 and beyond					
		Days -28 to 1	Day 1 Baseline	Day 8	Day 15	Day 22	Day 1	Day 8	Day 15	Day 22	Day 1	Day 8	Day 15	Day 22	
Demographic/baseline Assessments															
Informed consent	X														
Demography	X														
Inc./Exc. criteria	X														
Medical history	X														
MM diagnosis/history	X														
Internal Staging System (ISS)*****	X														
Cytogenetics (FISH) at study entry****	X														
Randomization	X														
Safety Assessments															
Physical examination	X	Symptom-directed physical examination													
Vital signs	X	X	X	X	X	X		X		X			X	X	
Weight	X	X	X	X	X	X		X		X			X	X	
Performance status score (ECOG)	X	X				X				X			X		
Adverse Events	Continuously until 30 days after last study treatment														
Concomitant medication, transfusions	X	X	X	X	X	X	X	X	X	X	X	X	X	X	
FEV1**	X														
ECG	X	As clinically indicated												X	
Lab Assessments*****															

Day of Cycle (28-days)	Screening	Treatment: visit window during the treatment period is +/- 3 days												End of treatment EOT ¹²	Survival follow-up Every 12 weeks					
		Cycles 1 and 2				Cycles 3-6				Cycles 7 and beyond										
		Days -28 to 1	Day 1 Baseline	Day 8	Day 15	Day 22	Day 1	Day 8	Day 15	Day 22	Day 1	Day 8	Day 15	Day 22						
Blood Type, Rh, and Indirect Antiglobulin Test (IAT) (DaraPomDex group only) ⁸		Prior to dosing on C1D1 only																		
Hematology ⁹	X	X	X	X	X	X		X		X				X						
Clinical chemistry ⁹	X	X		X		X				X				X						
Creatinine clearance	X	X				X				X				X						
Pregnancy test ¹	X	X				X				X				X						
Serum β 2-microglobulin, LDH	X																			
Hepatitis B serology ¹⁴	X																			
HBV-DNA testing ¹⁵	X						Every 12 weeks (window \pm 7 days)								X					
Daratumumab PK and Immunogenicity (DaraPomDex group only)	For subjects receiving daratumumab via subcutaneous administration refer to Section 7.3.1 ; for subjects who started daratumumab via IV infusion and switched to daratumumab subcutaneous administration, refer to Appendix 9 ; for subjects who receive Dara IV, only, refer to Appendix 10																			
Efficacy Assessments	Efficacy / Disease Assessment required to confirm response or disease progression should be performed as soon as possible after response or disease progression is suspected ¹⁶ – see Section 7.1 for details) After the primary clinical cut-off date (21 JUL 2020), subject monitoring will be conducted as per Section 7.2.4																			
SPEP, UPEP ^{2, 10}	X	X				X				X				X	X					
sIFE, uIFE ^{3, 10}	X	X				X			X				X	X						
sFLC assay, κ/λ ratio ^{4, 10}	X	X				X			X				X	X						
DSIFE *		To confirm a CR or better in subjects with IgG kappa myeloma when daratumumab interference is suspected based on SPEP- and sIFE results. See Section 7.1.1.3 .																		
Plasma cell count in bone marrow	X	Plasma cell count during the study as clinically indicated to qualify for CR. See Section 7.1.1.4 .																		
Bone marrow aspirates (Biomarker analysis)	X	At suspected CR and at PD (if feasible).																		
MRD*, ¹³	X	At suspected CR and, 6, 12, 18, 24 months post CR/sCR and every 12 months (yearly assessments \pm 3 months) thereafter in subjects with CR until PD. Assessment done by NGS. See Section 7.1.1.7 .																		
Whole blood for biomarker assessments		X	Whole blood for plasma, PBMCs and immunophenotyping may be collected predose at C3D1, C6D1, C12D1 and at suspected CR and at PD.																	
Corrected calcium ^{6, 10}	X	X				X				X			X	X						
Skeletal survey	X	As clinically indicated; CT/MRI in case of newly symptomatic areas with no X-ray finding. See Section 7.1.1.6 .																		

Day of Cycle (28-days)	Screening	Treatment: visit window during the treatment period is +/- 3 days												End of treatment EOT ¹²	Survival follow-up Every 12 weeks	
		Cycles 1 and 2				Cycles 3-6				Cycles 7 and beyond						
		Days -28 to 1	Day 1 Baseline	Day 8	Day 15	Day 22	Day 1	Day 8	Day 15	Day 22	Day 1	Day 8	Day 15	Day 22		
Assessment of extramedullary soft tissue plasmacytoma (STP)	X															
Response assessment by Investigator		X					X				X				X	X
PROs assessments (EQ-5D-5L, EORTC QLQ-C30, EORTC QLQ-MY20)		X					X				X				X	X
Treatment																
Daratumumab ¹²		X	X	X	X	X			X		X					
Pre- and post-infusion medications for daratumumab subjects		X	X	X	X	X			X		X					
Pomalidomide		4 mg PO on days 1-21 of each 28-day cycle														
Dexamethasone		X	X	X	X	X	X	X	X	X	X	X	X			
		40 mg (20 mg for subjects \geq 75 years of age) orally, weekly														
Other anti-neoplastic therapies		Not permitted												X	X	X
Survival follow-up***																X

Note: Pharmacokinetic/immunogenicity sample collection times for subjects receiving daratumumab via subcutaneous administration is provided in [Table 7.3.1](#); for subjects who started daratumumab via IV infusion and switched to daratumumab subcutaneous administration, refer to [Appendix 9](#); for subjects who receive Dara IV, only, refer to [Appendix 10](#).

Note: The majority of screening assessments are to be performed within 28 days of C1D1.

¹ For WOCBP only, 2 pregnancy tests, one 10 - 14 days prior to start of study drug and one within 24 hours prior to start of study drug. Urine tests must have a sensitivity of \geq 25 mIU/mL. WOCBP must have a pregnancy test 28 days after end of treatment.

² M-protein by electrophoresis in serum (SPEP) and urine (UPEP). Serum on Day 1 of each cycle until disease progression. 24-hour urine sample can be collected within \pm 7 days of visit.

³ M-protein by immunofixation in serum (sIFE) and urine (uIFE). A daratumumab-specific IF (DSIFE) is to be used when daratumumab interference is suspected based on SPEP and sIFE results.

⁴ Free light chain protein assessment (sFLC).

⁵ Subjects who discontinue treatment for reasons other than disease progression, death, lost to follow-up, or withdrawal of consent should continue to be followed for response assessments every 4 weeks. Note, however, that **all patients receiving Daratumumab** must attend for visits at 4 and 8 weeks post discontinuation of treatment (regardless of discontinuation reason) in order to undergo PK sampling as per [Table 7.3.1](#).

⁶ Corrected calcium will be also performed as clinically indicated to confirm disease progression.

⁷ Sample must be sent to central laboratory.

⁸ It is required that, in addition to ABO and Rh blood typing, the indirect antiglobulin test (also known as Indirect Coombs Test) be performed and that the subject carries an identification wallet card with these results at all times during the study. These tests will be conducted at the local laboratory. Blood type, Rh, and IAT should be done before the first dose of daratumumab. Subject RBC phenotyping (standard or extended) is an alternative option to the IAT test, if locally required. Either method must be completed prior to first daratumumab infusion.

*Examinations to be performed at central laboratory.

**Subjects with known or suspected COPD must have an FEV test during Screening.

***Subjects to be followed for 5 years for secondary primary malignancies.

****Examination to be performed at local laboratory, if available, or at the Erasmus laboratory.

***** For sites where β 2-microglobulin is measured locally, the local assessment of serum albumin (instead of the one measured centrally) will be used to determine the ISS stage.

***** Unless otherwise stated, all blood and urine samples must be obtained before administration of study treatment.

⁹ Hematology and clinical chemistry tests may be performed up to 3 days before the study treatment administration day. Laboratory assessments do not need to be repeated if done within 7 days of C1D1. Complete blood counts should be monitored at baseline, weekly for the first 8 weeks and monthly thereafter.

¹⁰ Disease assessments SPEP, UPEP, and serum calcium corrected for albumin, should be collected every cycle for the first 14 months of the study and every other month thereafter. After Cycle 1, IFE should only be done when endogenous M-protein is 0 or nonquantifiable. For subjects who are followed by FLC only, these assessments are performed every other cycle after 14 months.

¹¹ Every effort should be made to follow the planned dosing schedule; however, doses within 3 days of the scheduled dose will be permitted. Subjects should start study treatment within 3 days after randomization. The dose does not need to be recalculated for weight changes that are <10% from baseline.

¹² EOT visit to occur 4 weeks after the last dose of study treatment or as soon as possible before the start of subsequent therapy.

¹³ In the event a fresh screening biopsy/aspirate cannot be collected, use non-decalcified diagnostic tissue (ie, bone marrow aspirate, touch preparation, or clot selection) or formalin-fixed paraffin embedded (FFPE) block (clot selection only, no bone marrow biopsy) from a sample taken within 42 days from C1D1.

¹⁴ All subjects will be tested at screening for hepatitis B surface antigen (HBsAg), hepatitis B surface antibody (anti-HBs), hepatitis B core antibody (anti-HBc).

¹⁵ Only in subjects who are positive for antibodies to hepatitis B core antigen [antiHBc] and/or antibodies to hepatitis B surface antigen [antiHBs]. Subjects with serologic findings suggestive of HBV vaccination (antiHBs positivity as the only serologic marker) AND a known history of prior HBV vaccination do not need to be tested for HBV-DNA by PCR.

¹⁶ Following the positive primary analysis of PFS, disease evaluations are to be performed locally per the site's standard of care. All subjects must still meet IMWG criteria for progression prior to initiation of subsequent anti-myeloma therapy. Notification of PD and approval by the Sponsor is no longer required.

Table 7.3.1: Schedule of Events: Pharmacokinetic/Immunogenicity Sample Collection Times for Subcutaneous Daratumumab Subjects

Days of Cycle (28-days)	Cycle 1		Cycle 3		Cycle 5	Cycle 7	Cycle 12	Follow-up	
Day	1	4	1	4	1	1	1	Post-treatment Week 4	Post-treatment Week 8
Visit Window	0	+/- 1 day	+/- 1 day	+/- 1 day	+/- 3 days	+/- 3 days	+/- 3 days	+/- 7 days	+/- 7 days
Daratumumab PK (serum)	X (Predose) ¹	X	X (Predose) ¹	X	X (Predose) ¹	X (Predose) ¹	X (Predose) ¹	X	X
Daratumumab Immunogenicity (serum)	No additional sample required; taken from Daratumumab PK Sample								
rHuPH20 immunogenicity (plasma)	X (Predose) ^{1,2}				X (Predose) ^{1,2}	X (Predose) ^{1,2}	X (Predose) ^{1,2}	X	X

rHuPH20=recombinant human hyaluronidase.

¹ On dosing days, sample collection may occur up to 2 hours before but not after the start of drug administration. Samples collected on dosing days with visit windows must be collected on the actual day of study drug administration. Samples collected on non-dosing days should be collected within ± 4 hours of the time of day the drug administration was started on the most recent dosing day.

² In addition, samples for assessment of antibodies to daratumumab and rHuPH20 should be drawn, if possible, any time an infusion-related reaction is reported (according to laboratory manual and [Section 7.1.4.4](#)) in association with the second administration or beyond.

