Drug administration and follow-up visits will occur more frequently for early cycles (eg, weekly or bi-weekly) (see [Table 7.3](#)). Disease evaluations will occur every cycle and consist mainly of measurements of myeloma proteins. Other parameters may include bone marrow examinations, skeletal surveys, assessment of extramedullary plasmacytomas, and measurements of serum calcium corrected for albumin. Patient reported outcome measures will be administered on Day 1 of each treatment cycle, prior to receiving treatment or any other assessment. The schedule of assessments will be adjusted for subjects remaining on study after the positive primary analysis and is detailed in [Section 7.2.4](#). A schedule of assessments is provided in [Appendix 12](#) (and detailed in [Table 7.3](#)) for subjects continuing on study treatment after the CCO for the final OS analysis.

Assessment of myeloma response and disease progression will be conducted in accordance with the modified IMWG response criteria.

Survival status, subsequent anti-myeloma treatment data, and PRO measures will continue to be collected post-treatment.

The primary analysis of PFS will occur after 188 PFS events have been observed. Long-term survival follow-up and data collection will continue until approximately 166 deaths have been observed or 5 years after the last subject is randomized, whichever occurs earlier. Subjects benefiting from the study treatment can continue to receive study treatment after the CCO for the final OS analysis. For these subjects, study treatment will be available through continued access within the current study until it is available through another source such as commercial availability with reimbursement, continued access through a long-term extension study, a patient access program, or after the last subject transitions into the long-term extension phase of the study up to 30 September 2024, whichever occurs first.

Figure 4.1: Study Design

*The schedule of assessments will be adjusted for subjects remaining on the study after the positive primary analysis and is detailed in *Section 7.2.4*. A schedule of assessments is provided in *Appendix 12* (and detailed in *Table 7.3*) for subjects continuing on study treatment after the CCO for the final OS analysis.

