6.1.6 Duration of Therapy

Treatment with study drug continues until disease progression, unacceptable toxicity (AE related to study drug), or the subject meets other criteria for discontinuation of study drug outlined in [Section 5.3](#).

The Sponsor will ensure that subjects who are benefiting from study treatment can continue to receive study treatment after the CCO for the final OS analysis. For these subjects, study treatment will be available through continued access within the current study until it is available through another source such as commercial availability with reimbursement, continued access through a long-term extension study, a patient access program, or after the last subject transitions into the long-term extension phase of the study up to 30 September 2024, whichever occurs first.

The long-term extension phase of this study will begin at the time of the CCO for the final OS analysis and is intended to provide ongoing access to study treatment for subjects who continue to benefit from such treatment. Certain long-term safety data will continue to be reported for these subjects, as described in [Appendix 12](#).

No eCRF data will be collected after the CCO date for the final OS analysis (when approximately 166 deaths have been reported). All eCRF data collected up to this timepoint will be included in the final study analysis and reported in a separate clinical study report.

The investigational sites are requested to notify the Sponsor within 1 working day if a subject has been diagnosed with disease progression (that is also confirmed with a consecutive assessment if based on M-protein/serum FLC levels) and provide documentation of disease progression. The Sponsor's medical monitor will review the data provided to confirm that the IMWG criteria for PD have been met, refer to [Section 7.1.1](#) (Sponsor Confirmation of Progressive Disease). For subjects continuing the study after the positive primary analysis, notification of PD and approval by the Sponsor is no longer required. Please refer to [Section 7.1.1](#) (Sponsor Confirmation of Progressive Disease) for updated procedures.

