7.2.3 Follow-up Period

Post-treatment Follow-up

Subjects who discontinue treatment for reasons other than documented disease progression, death, lost to follow-up, or withdrawal of consent should continue to be followed for response assessments every 4 weeks as in [Table 7.3](#). The reason for completion/discontinuation should be recorded on the eCRF.

If a subject starts new anti-myeloma therapy prior to disease progression, every attempt should be made to perform tumor evaluations until documented disease progression. In addition, all new anti-neoplastic therapy administered starting from the last dose of the study treatment until death, lost to follow-up, or withdrawal of consent will be recorded in the eCRFs.

Survival Follow-up

Subjects will be followed every 12 weeks, or more frequently, after disease progression for survival and subsequent myeloma therapy.

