7.2.4 Updated Assessments Following the Positive Primary Analysis of PFS

Following the positive primary analysis of PFS, subjects remaining in the study will continue to be monitored as follows until the final analysis (ie, when approximately 166 deaths have occurred or 5 years after the last subject was randomized). Subjects benefiting from the study treatment can continue receiving the study drugs after the end of data collection until the study drugs are commercially available and reimbursable, available from another source (eg, via a dedicated long-term extension study), or until study completion, whichever comes first.

Subjects who have had Disease Progression

For subjects whose disease has progressed, every-12 week follow-up contacts should continue to be performed to capture the following:

- Survival
- Subsequent anti-myeloma therapy
- New second primary malignancies

Data may be collected directly from subject or indirectly (eg, from medical correspondence or remote/telephone visits).

Subjects who Have not had Disease Progression

Following the positive primary analysis of PFS, disease evaluations are to be performed locally per the site's standard of care. All subjects must still meet IMWG criteria for progression prior to initiation of subsequent anti-myeloma therapy.

Pharmacokinetic and Immunogenicity Assessments for DPd arm

After the positive primary analysis, a limited schedule of PK and immunogenicity assessment will be implemented to reduce the burden of blood sampling in subjects. For subjects who receive daratumumab by SC administration starting from the first dose and subjects who received daratumumab initially by IV then switched to SC, samples are to be collected for PK and immunogenicity assessments at EOT and 8 weeks after the last dose of daratumumab, regardless of whether there has been confirmed disease progression. No subjects remain on daratumumab IV at the time of positive primary analysis and beyond. In addition, 2 separate blood samples should be obtained, if possible, for the assessment of antibodies to daratumumab and rHuPH20 any time an infusion-related reaction is reported in a subject receiving Dara SC in association with the second administration or beyond. Daratumumab serum concentration will also be determined from the daratumumab infusion reaction sample for the purpose of interpreting immunogenicity data.

Study procedures

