8.4.3 Events of Special Interest

Safety events of special interest include, but are not limited to:

- Secondary Primary Malignancies
- Infusion-Related Reactions
- Medication Error
- Abuse/Misuse/Overdose
- Occupational Exposure
- Drug-Drug Interaction
- Suspected Transmission of Infectious Agents
- Intravascular Hemolysis

All events of special interest should be monitored and recorded in the eCRF. Any event that meets the criteria of a serious adverse event should be recorded on the eCRF. In addition, any events of secondary primary malignancies and suspected transmission of infectious agents will follow the same SAE reporting timelines and procedures outlined in [Section 8.4.2](#).

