Efficacy Evaluations

Investigators will monitor and assess subjects for response to treatment or disease progression according to local institutional practice. The assessments and outcome should be entered in the subject file/source notes.

Safety Reporting

For subjects continuing study treatment after the CCO date for the final OS analysis, SAEs that occur while the subject is receiving study treatment and within 30 days after the last dose of study treatment will be collected on paper-based SAE forms and reported to the Sponsor's global medical safety database with the same information that has been collected on the eCRF, however, SAE notification can be carried out by contacting a Pharmacovigilance Officer via email at [contact] or by fax using the following number: [contact] (or updated contact information supplied by the Sponsor if the email address and/or fax number change during the conduct of the study). SAEs that occur between the 30-day post-dose period and completion of the study should be reported using the same process if considered by the investigator to be related to study treatment. SAEs should also be documented in the subject file/source notes.

Pregnancy reporting should continue as described in [Section 8.4.4](#). The pregnancy should be documented in the subject file/source notes.

Sample Collection and Handling

For subjects continuing study treatment after the CCO date for the final OS analysis, there will be no study-related assessments performed during this treatment period, and any sample collection or test for safety or disease evaluation performed by the sites for patient management should comply with standard local institution practice.

Case Report Form Completion

No data will be collected in the eCRF during this treatment period.

Source Documentation

At a minimum, the type and level of detail of source data collected should include: subject and study identification, study discussion, documentation of the informed consent process including the date, dates of visits, drug dispensing/return records, study treatment administration information, and study treatment discontinuation information (including date and reason for discontinuation).

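### The Table 7.3 footnote promises 5 years of second primary malignancy follow-up, but collection stops at the final OS cutoff, so 5 years is not secured

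*Combined protocol and SAP*

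**What the plan says.** Second primary malignancies (SPMs) are listed as an event of special interest in Section 8.4.3. The footnote marked with three asterisks on the survival follow-up row of Table 7.3 reads "Subjects to be followed for 5 years for secondary primary malignancies". It attaches no condition and gives no starting point.

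Other sections set when collection ends:

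- Section 4.1 and the Protocol Summary continue survival follow-up and data collection "until approximately 166 deaths have been observed or 5 years after the last subject is randomized, whichever occurs earlier".
- Section 6.1.6: "No eCRF data will be collected after the CCO date for the final OS analysis (when approximately 166 deaths have been reported"). This section mentions only the death count.
- Section 7.2.4 runs the post-primary-analysis monitoring "until the final analysis (ie, when approximately 166 deaths have occurred or 5 years after the last subject was randomized"). For progressed subjects, the 12-week contacts include "New second primary malignancies".
- Section 7.2.3 describes survival follow-up without SPMs: "Subjects will be followed every 12 weeks, or more frequently, after disease progression for survival and subsequent myeloma therapy".
- Appendix 12, for subjects who stay on treatment after the cutoff: "No data will be collected in the eCRF during this treatment period". It also declares protocol-defined post-treatment follow-up not applicable to them.

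Section 8.4.3 adds a reporting route: "any events of secondary primary malignancies and suspected transmission of infectious agents will follow the same SAE reporting timelines and procedures". Under Section 8.4.2, SAEs arising more than 30 days after treatment are reported only if the investigator suspects a causal link. Sections 7.3.7 and 14.5 end the study no later than 30 September 2024.

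**The concern.** The footnote states a fixed period of SPM follow-up. The rest of the protocol ends collection at a date set by deaths, with a calendar limit counted from the last randomization. The two agree for a given subject only if the cutoff happens to fall at least 5 years after that subject's clock starts, and the protocol does not define that start.

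The subjects affected are survivors, in whom late malignancies can still appear. If follow-up is cut at the OS cutoff and the report repeats the protocol's 5 years, readers will take the SPM data as more mature than they are. Follow-up may also differ between arms if survival does, so crude counts without the follow-up distribution would be hard to compare.

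**Working it through.** **Step 1. What the text secures, without any survival assumption.**

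| Possible start of the 5 years | What the protocol secures |
|---|---|
| Randomization | The last-randomized subject gets exactly 5 years if 166 deaths have not occurred by then, and less if they have. Earlier-randomized subjects get more. |
| Progression or end of treatment | Less than 5 years for the last-randomized subject whenever the clock starts after randomization. |

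The second row has a hard limit. From the primary cutoff (21 July 2020, Table 7.3) to the latest study end (30 September 2024) is 50.3 months. A clock that starts after 21 July 2020 cannot reach 60 months within the study, even if collection ran to study end. Collection in fact stops at the CCO.

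**Step 2. When 166 deaths might occur.** The documents give no OS median, accrual period or projected OS cutoff date for this trial.

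Inputs from Section 10.5: 302 subjects, 151 per arm, HR 0.66, 166 deaths. Assumptions: exponential survival, uniform accrual over A months, no early censoring, and the control medians tabulated below.

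With λ = ln 2 / control median, and t months since the first randomization (t ≥ A):

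F(t; λ) = 1 − [exp(−λ(t − A)) − exp(−λt)] / (λA)

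Deaths(t) = 151 × [F(t; λ) + F(t; 0.66λ)], solved for 166.

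Example with median 36, A = 12, t = 57: 151 × (0.6246 + 0.4765) = 166.3.

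| Control median (months) | A | From first randomization | From last randomization |
|---|---|---|---|
| 12.7 (Phase 3 PomDex study, Section 2.2) | 12 / 30 | 24.2 / 34.6 | 12.2 / 4.6 |
| 16.5 (Phase 2 PomDex study, Section 2.2) | 12 / 30 | 29.5 / 39.6 | 17.5 / 9.6 |
| 24 (illustrative) | 12 / 30 | 40.0 / 49.8 | 28.0 / 19.8 |
| 36 (illustrative) | 12 / 30 | 56.9 / 66.4 | 44.9 / 36.4 |

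**Step 3. Check the projection against the protocol's own dates.** Amendment 4, dated 21 April 2022, still describes the 166-death cutoff as ahead. That is 60.5 months after the original protocol (7 April 2017). Some subjects had started Dara IV before Amendment 1, so take its issue date, 13 October 2017, as the latest start (an assumption, since approval may have come later). The first subjects were then at least 54.2 months from randomization.

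Deaths expected at 54.2 months, for A of 12 and 30 months:

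- median 12.7: 264 and 244
- median 16.5: 242 and 219
- median 24: 204 and 179
- median 36: 160 and 138

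The first three medians all predict more than 166 deaths by then and so do not fit the amendment date. Taking accrual to start between April and October 2017 and to end between April 2018 and July 2020 (assumed), fewer than 166 deaths by 21 April 2022 implies a control median of at least about 26 to 39 months.

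**Step 4. Consequence.** With a median of 36 months, which fits the October 2017 start, the cutoff falls 57 to 66 months after the first randomization and 36 to 45 months after the last. The earliest subjects can reach 5 years. The latest fall short by about 60 − 45 = 15 to 60 − 36 = 24 months.

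**The case against.** The strongest reply has four parts.

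- **The cutoff may not be early.** A reader might take the PomDex medians in Section 2.2 and infer that the cutoff comes well before 5 years and that no subject reaches 5 years. The documents do not support this. Those medians are results of earlier studies in refractory or relapsed-and-refractory disease, not assumptions for this trial, which admits subjects after one prior line. Step 3 shows that they conflict with the date of Amendment 4. This part of the reply stands in full.
- **Reporting does not stop at the cutoff.** A reader might also infer that all SPM reporting ends with the eCRF. It does not. Appendix 12 keeps a paper SAE route for subjects on treatment and for 30 days after, and later for related events. Section 8.4.3 puts SPMs on the SAE route, and Section 8.4.2 covers later SAEs suspected to be related. This stands, but spontaneous reporting of suspected-related events is not scheduled ascertainment. It misses malignancies judged unrelated, and it gives no confirmed malignancy-free follow-up time for off-treatment subjects.
- **The table already qualifies the footnote.** The note heading Table 7.3 says that eCRF collection ends at the CCO. That is true, but it leaves the conflict in place: one table gives both an unconditional 5 years and an earlier stop.
- **The harm is hypothetical.** No endpoint or planned safety analysis in Section 10.4.4 claims 5-year SPM follow-up. This stands as a limit on severity. The issue concerns how follow-up is described, not a planned test.

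**Conclusion.** The point holds as an internal inconsistency of minor severity. The footnote states 5 years of SPM follow-up, and the design does not secure it. No starting point is defined, collection ends at the CCO, and no scheduled SPM contact is described afterwards for subjects off treatment.

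The size depends on the starting point. Counted from randomization, the last subjects would have about 36 to 45 months in the illustrative case. That range rests on exponential survival, a 36-month control median, HR 0.66, uniform accrual over 12 to 30 months and no early censoring. Early-randomized subjects may reach about 5 years. Counted from progression or end of treatment after 21 July 2020, 5 years is impossible before study end. That conclusion needs only the protocol's dates.

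**What to change.** Reconcile the Table 7.3 footnote with Sections 4.1, 6.1.6 and 7.2.4 and Appendix 12. State that SPMs are followed from randomization until the CCO for the final OS analysis, and use the same full stopping rule in each place (Section 6.1.6 now gives only the death count). In the report, give SPMs per 100 patient-years by arm with the actual distribution of follow-up time in each arm, and make no claim of 5-year follow-up. Naming SPMs again in Appendix 12 would add little, because Section 8.4.3 already places them on the SAE route.

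The cost is a wording change and one added table. The stated follow-up becomes less favourable.
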